12.3 Approximate Blood/Tissue Volumes Drawn/Collected by Trial Visit and by Sample Types

Panels A, B, and C	Pre-trial	Treatment Periods	Post-trial	Total Collections	mL Per Collection	Total mL/ Test
Laboratory safety tests [‡]	1	3	1	5	10.2	51
Blood for Planned Genetic Analysis		1		1	8.5	8.5
Blood for TFV assays and MK-8583		12		12	4	48
Blood for PBMC assay		10	1	11	16	176
Blood for HIV RNA, viral resistance [§]	1	10	1	12	12	144 [%]
Total Blood Volume Per Subject [†]						427.5
[†] If additional pharmacokinetic/pharmacodynamic and/or safety analysis is necessary, up to 50 mL of additional blood may be obtained. [‡] Blood for Serum β -Human Chorionic Gonadotropin (β -hCG), HIV/Hepatitis screen, FSH, and CD4 cell count are included in the Laboratory Safety blood draw volume. [§] For all panels blood for HIV-1 viral RNA and viral resistance may be collected up to the post-trial visit if subjects do not start ART. [%] An additional 4 mLs of blood may be drawn at 168 hours post-dose if ultra-deep sequencing is needed. [*] Sample may be urine OR serum						

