3.2 Secondary Objective(s) & Hypothesis(es)

- 1) **Objective:** To evaluate the intracellular PK profile of TFV-DP and to determine PK parameter values (including AUC_{0-168hr}, T_{max}, C_{max}, C_{168hr}, and apparent terminal t_{1/2}) in PBMCs after administration of single oral doses of MK-8583 to HIV-1 infected subjects.

Hypothesis: The true geometric mean (GM) TFV-DP PBMC C_{168hr} is $\geq 0.1 \mu\text{M}$ for at least one dose level that also exhibits an acceptable safety and tolerability profile.

- 2) **Objective:** To characterize the single dose plasma PK profile of MK-8583 and to determine the PK parameter values (including AUC_{0-last}, AUC_{0-inf}, T_{max}, C_{max}, apparent terminal t_{1/2}, CL/F and V_z/F) after administration of MK-8583 to HIV-1 infected subjects.
- 3) **Objective:** To obtain the single dose plasma PK profile of TFV and to determine the PK parameter values (including AUC_{0-last}, AUC_{0-inf}, T_{max}, C_{max}, and apparent terminal t_{1/2}) after administration of MK-8583 to HIV-1 infected subjects.
- 4) **Objective:** To evaluate the PK-PD association of TFV-DP with viral load reduction.

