MK-8583 was assessed in a single rising-dose study in healthy subjects. Following oral administration, MK-8583 was rapidly absorbed (time to maximum plasma concentration [T_{max}] ~ 0.5 hour) and rapidly eliminated from the plasma (terminal half-life [t_{1/2}] of 0.2 to 0.4 hours). Prodrug exposure was dose-proportional at doses ≥ 40 mg. Plasma TFV exposure was also dose-proportional, with a T_{max} of 1 to 4 hours and a t_{1/2} in the range of 19 to 30 hours. TFV-DP in PBMCs exhibited a median T_{max} of 4 to 24 hr and a terminal t_{1/2} ranging from 65 to 136 hours. The PBMC TFV-DP AUC increased approximately dose-proportionally, and the C_{max} increased somewhat more than dose-proportionally. Food somewhat lowered peak and extent of exposure of PBMC TFV-DP (GM fed/fasted ratio of 0.83 for AUC_{0-inf}, 0.32 for maximum concentration [C_{max}], 0.47 for C_{168hr}). Elimination of plasma MK-8583 was monophasic, while elimination of plasma TFV was biphasic. PBMC TFV-DP presented monophasic elimination, but showed signs of biphasic elimination at higher doses.

Single oral doses of MK-8583 up to 150 mg were generally well tolerated. No SAEs, events of clinical interest (ECIs), or deaths were reported. A total of 24 subjects enrolled in the trial. No trends were observed between AE incidence and increasing dose levels, and there were no AE findings consistent with renal or bone toxicity. No clinically meaningful trends were observed for changes in clinical laboratory values, vital signs (VS), or ECGs as a function of dose or treatment.

Please refer to the Investigator's Brochure (IB) for more detailed information on MK-8583.

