The AUC_{0-168hr} was selected as the relevant exposure parameter, instead of C_{max}, because the preclinical toxicity of MK-8583 was associated with chronic dosing and was similar to clinical toxicity observed with chronic dosing of marketed TFV prodrugs. (The mean TFV C_{max} at the preclinical NOAEL and at the maximum clinical dose of 150 mg were 102 nM and 175 nM, respectively. The mean MK-8583 C_{max} at the preclinical NOAEL and at the maximum clinical dose of 150 mg were 168 nM and 1,074 nM, respectively.)

TFV Exposure Multiple: Comparing the TFV AUC_{0-168hr} at the dog NOAEL (17,850 nM*hr at 3 mg/kg/day) to that of the rat (446,000 nM*hr at 150 mg/kg/day), the dog represents the more sensitive species. Therefore, the maximum allowable exposure is based on the TFV AUC_{0-168hr} at the NOAEL of the dog, in this case 17,850 nM*hr. In healthy subjects, the maximum dose of 150 mg yielded a TFV AUC_{0-inf} (approximately equal to the AUC_{0-168hr}) of 3836 nM*hr; the preclinical safety data provide a 4.7-fold exposure margin (EM) (see [Table 2](#)).

MK-8583 Exposure Multiple: Whereas the plasma protein binding of TFV is minimal across all species, there are significant inter-species differences in the protein binding of MK-8583 (~70-80% in rat, ~93-95% in human and dog). The total MK-8583 AUC_{0-168hr} at the dog NOAEL (620 nM*hr at 3 mg/kg/day) and at the rat NOAEL (540 nM*hr at 150 mg/kg/day) are similar. But comparing the unbound MK-8583 AUC_{0-168hr} at the dog NOAEL (29.8 nM*hr at 3 mg/kg/day) to that of the rat (96.6 nM*hr) identifies the dog as the more sensitive species. In healthy subjects, the maximum dose of 150 mg yielded an MK-8583 AUC_{0-inf} (approximately equal to the AUC_{0-168hr}) of 684 nM*hr, which is 0.9-fold that of the MK-8583 AUC at the dog NOAEL (620 nM*hr, see [Table 2](#)).

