6.0 TRIAL FLOW CHART

	Panels A, B, and C																		
	Scheduled Time																		
	Prestudy	Pre-dose	0	0.25	0.5	1	2	4	6	12	24	36	48	72	96	168	240	312	672/Post-trial ^a
Administrative Procedures																			
Informed Consent	X																		
Informed Consent for Future Biomedical Research	X																		
Inclusion/Exclusion Criteria	X	X																	
Subject Identification Card	X																		
Medical History	X																		
Assignment of Screening Number	X																		
Assignment of Randomization Number ^c		X																	
Prior/Concomitant Medication Review	X	X																	X
Subject domiciling in the clinical research unit		X								X									
Clinic Procedures/Assessments																			
Full Physical Examination (PE)	X	X ^d														X			X
Height	X																		
Weight	X																		
12-Lead Electrocardiogram ^e	X	X				X				X						X			X
Vital Signs (heart rate, blood pressure, respiratory rate, body temperature) ^f	X	X				X				X						X			X
Orthostatic Vital Signs (heart rate, blood pressure) ^f	X	X				X				X						X			X
Standard Meals ^g									X		X								
MK-8583 Administration			X																
Adverse Events Monitoring	X																		X
Laboratory Procedures/Assessments																			
Laboratory Safety Tests (hematology, chemistry, urinalysis)	X	X ^d								X						X			X
Urine /Serum β-Human Chorionic Gonadotropin (β-hCG) ^h	X	X ^d																	X
Serum FSH ⁱ	X																		
Urine/Blood Drug Screen ^j	X	X ^d																	
HIV/Hepatitis Screen	X																		
Blood for Genetic Analysis ^b		X																	

		Panels A, B, and C																	
		Scheduled Time																	
		Hours Post-dose																	
	Prestudy	Pre-dose	0	0.25	0.5	1	2	4	6	12	24	36	48	72	96	168	240	312	672/Post-trial ^a
Stool for Future Biomedical Research ^o		X																	
Pharmacokinetic/Pharmacodynamic Evaluations																			
Blood for Plasma MK-8583 and TFV Assay ^k		X		X	X	X	X	X	X	X	X	X	X	X					
Blood for MK-8583 PBMC Assay ^{l,n}		X						X		X	X		X	X	X	X	X	X	X
Blood for HIV RNA, Viral Resistance ^{m,n}	X	X						X		X	X		X	X	X	X	X	X	X
CD4-positive cell count	X																		

		Panels A, B, and C																	
		Scheduled Time																	
		Hours Post-dose																	
	Prestudy	Pre-dose	0	0.25	0.5	1	2	4	6	12	24	36	48	72	96	168	240	312	672/Post-trial ^a

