mean change from baseline at 168 hours will be generated using flat priors under a normal likelihood assumption. Using the posterior distributions for each dose level and placebo, the posterior distribution of the true mean difference between each dose level and placebo will be generated, and the posterior probability that the true mean difference in the log₁₀ plasma HIV-1 RNA reduction from baseline between MK-8583 and placebo is at least 0.5 log₁₀ copies/mL will be calculated. An 80% posterior probability for at least one dose level that also exhibits an acceptable safety and tolerability profile will satisfy the primary PD hypothesis. For each dose level, the posterior probability that the true mean log₁₀ plasma HIV-1 RNA reduction from baseline is at least 0.5 log₁₀ copies/mL will also be calculated. Similar exploratory analyses may be performed using viral load measurements at baseline and specified post-baseline time points.

Secondary (Pharmacokinetics)

Separately for each PK parameter, individual values of TFV-DP in PBMC PK parameters AUC_{0-168hr}, C_{max}, and C_{168hr} from subjects in all panels will be pooled, natural log transformed and analyzed based on a linear model containing a fixed effect for dose level. The 95% confidence intervals for the least squares means by dose level will be constructed on the natural log scale and will reference the t-distribution. Exponentiating the least-squares means and lower and upper limits of these confidence intervals will yield estimates for the population geometric means and confidence intervals about the geometric means on the original scale. The posterior probability that the true GM C_{168hr} PBMC TFV-DP level is $\geq 0.1 \mu\text{M}$ will be calculated for each dose level using flat priors under a normal likelihood assumption. An 80% posterior probability for at least one dose level that also exhibits an acceptable safety and tolerability profile will satisfy the secondary PK hypothesis.

MK-8583 plasma AUC_{0-last}, AUC_{0-inf}, C_{max}, CL/F and V_z/F, and TFV plasma AUC_{0-last}, AUC_{0-inf} and C_{max} will be analyzed in a similar fashion.

Descriptive Statistics

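### Plasma sampling stops at 72 h, which leaves the TFV terminal half-life imprecise in each subject; a TFV sample at the existing 96 h visit would improve it at little cost (minor)

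*Combined protocol and SAP*

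**What the plan says.** - **Schedule.** In the flow chart (Section 6.0), the row "Blood for Plasma MK-8583 and TFV Assay" is marked at pre-dose and at 0.25, 0.5, 1, 2, 4, 6, 12, 24, 36, 48 and 72 h. Nothing is marked at 96, 168, 240, 312 or 672 h.
- **Volume.** In Section 12.3, the row "Blood for TFV assays and MK-8583" gives 12 collections of 4 mL, 48 mL in all. The total per subject is 427.5 mL, and up to 50 mL more may be taken.
- **Kinetics.** Section 4.1.2 describes plasma TFV in healthy subjects "with a T_{max} of 1 to 4 hours and a t_{1/2} in the range of 19 to 30 hours" and adds that "elimination of plasma TFV was biphasic". The prodrug MK-8583 has a half-life of 0.2 to 0.4 h.
- **Aim.** Secondary objective 3 (Section 3.2) is "To obtain the single dose plasma PK profile of TFV and to determine the PK parameter values". The list that follows includes AUC0-inf and apparent terminal half-life. Section 8.2.2 makes both secondary endpoints. Section 8.2.4 says "TFV plasma AUC_{0-last}, AUC_{0-inf} and C_{max} will be analyzed in a similar fashion"; half-life is not in that modelled list.
- **Exposure limit.** Section 4.2.2.2 says that "the maximum allowable exposure is based on the TFV" AUC0-168hr at the dog NOAEL. Sections 4.2.2.1 and 4.2.2.2 treat clinical AUC0-inf as approximately equal to AUC0-168hr.
- **Existing visits.** PBMC and HIV RNA blood is already drawn at 96 h and 168 h.

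**The concern.** One plasma schedule serves two analytes with very different kinetics. It suits MK-8583, which has gone within a few hours. It is short for TFV, which is still declining at 72 h. In a biphasic decline the terminal slope must come from the late points only, and the schedule has few of them.

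What is at stake is the precision of the TFV terminal half-life, a named endpoint estimated in six subjects per panel. To a lesser degree it is also the part of AUC0-inf that has to be extrapolated with that slope. TFV is the analyte that the protocol links to toxicity, and Panel A PK is compared with Protocol 001 before Panel B. No plasma TFV is scheduled between 72 h and 168 h, so the trial cannot check for itself that AUC0-inf and AUC0-168hr agree.

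**Working it through.** **1. The plan's own volume.** 5 × 10.2 + 1 × 8.5 + 12 × 4 + 11 × 16 + 12 × 12 = 51 + 8.5 + 48 + 176 + 144 = 427.5 mL. This reproduces Section 12.3, and the 12 plasma collections match the 12 marks in the flow chart.

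**2. Half-lives covered by 72 h.** (72 − start) / half-life. The documents do not say when the terminal phase starts, so the start is varied.

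| Assumed start | Half-life 30 h | Half-life 19 h |
|---|---|---|
| 4 h (latest Tmax) | 2.3 | 3.6 |
| 12 h | 2.0 | 3.2 |
| 24 h | 48/30 = 1.6 | 48/19 = 2.5 |
| 36 h | 1.2 | 1.9 |

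**3. Precision of the half-life in one subject.** For a log-linear fit, CV ≈ (s / √Sxx) / k, where k = ln 2 / half-life (0.0231 per h at 30 h, 0.0365 at 19 h) and s is the residual SD on the log scale. The documents give no s; 0.10 to 0.20 is assumed. All fits start at 24 h.

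- 24, 36, 48, 72 h: mean 45, Sxx = 441 + 81 + 9 + 729 = 1,260, √Sxx = 35.5.
- With 96 h: mean 55.2, Sxx = 3,340.8, √Sxx = 57.8.
- With 96 h and 168 h: mean 74, Sxx = 13,944, √Sxx = 118.1.

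Example: s = 0.10, half-life 30 h, current schedule: (0.10 / 35.5) / 0.0231 = 12.2%.

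| Points used | CV at 30 h (s = 0.10 to 0.20) | CV at 19 h (s = 0.10 to 0.20) |
|---|---|---|
| 24-72 h (current) | 12.2-24.4% | 7.7-15.4% |
| plus 96 h | 7.5-15.0% | 4.7-9.5% |
| plus 96 h and 168 h | 3.7-7.3% | 2.3-4.6% |

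The 96 h point alone reduces the CV by 1 − 35.5/57.8 = 39%. The last row holds only if the 168 h value is quantifiable. If the 12 h point could also be used, the current CV would be 9.4-18.8% at 30 h and 5.9-11.9% at 19 h.

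**4. Share of AUC0-inf beyond 72 h.** If decline runs at the terminal rate from time 0, the share is 2^(−72/half-life): 7.2% at 19 h and 18.9% at 30 h. Counted from a 4 h Tmax, 2^(−68/half-life) gives 8.4% and 20.8%.

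As a cross-check, take a biphasic curve with A + B = 175 nM and A/a + B/b = 3,836 nM·hr. These are the 150 mg Cmax and AUC0-inf in Section 4.2.2.2. Absorption is ignored and the fast-phase half-life is assumed to be 2 to 6 h. With a 30 h terminal and a 4 h fast half-life, B = 75.3 nM. The tail is (75.3 / 0.0231) × 2^(−72/30) ≈ 617 nM·hr, and 617 / 3,836 = 16.1%. Over all cases the share is 6.4% to 17.6%. So about 80% to 94% of AUC0-inf is observed by 72 h.

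**5. Bias in the fitted half-life on those curves.** The 24-72 h fit returns 18.4-19.0 h when the truth is 19 h, and 26.5-30.0 h when it is 30 h. With 96 h and 168 h added it returns 18.8-19.0 h and 29.0-30.0 h.

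**6. Predicted TFV after 100 mg.** Scaling the curves by 2,380 / 3,836 (the 100 mg and 150 mg AUC0-inf) gives 5.6-9.7 nM at 72 h, 2.3-5.6 nM at 96 h and 0.2-1.1 nM at 168 h.

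**The case against.** The strongest reply is that little depends on this. No hypothesis concerns plasma TFV; the secondary PK hypothesis is on PBMC TFV-DP. TFV half-life is not modelled in Section 8.2.4, and Section 7.1.5.4 names viral load and PBMC samples as the critical ones. The comparison with Protocol 001 can also use Cmax and AUC0-last. Section 7.1.5.5 lets the PK scheme change on new data, and Section 2.1 allows further PK draws in some subjects.

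Most of this stands and sets the grade at minor. It does not remove the point. Half-life is still a stated objective and endpoint. Neither flexibility clause schedules plasma TFV after 72 h, and the only change in sampling length that Section 7.1.5.5 lists is a decrease.

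Three stronger readings are tempting, and the documents do not support them:

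- A reader might infer that AUC0-inf depends on the short window as much as half-life does. It does not: step 4 shows that only the last 6% to 21% depends on the slope.
- A reader might infer that the exposure limit or dose selection is at risk. Table 2 gives TFV multiples of 7.5 at 100 mg and 4.7 at 150 mg. If true TFV AUC were 20% higher than measured, they would still be 7.5/1.2 = 6.25 and 4.7/1.2 = 3.9. The thin multiple in Table 2 (0.9 at 150 mg) is for MK-8583, which sampling to 72 h covers fully.
- A reader might infer that a slower late TFV phase is being missed, because Section 4.1.2 says TFV leaks from target cells and gives PBMC TFV-DP a half-life of 65 to 136 h. That is plausible but remains inference: the same section reports plasma TFV as biphasic with 19 to 30 h and no slower phase. If one existed, the shares in step 4 would be too low.

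**Conclusion.** The point holds as a minor matter of precision. Under the current schedule the per-subject CV of the TFV terminal half-life is about 12-24% at a 30 h half-life and 8-15% at 19 h. With a 96 h sample it is about 7-15% and 5-9%. These figures rest on two assumptions that the documents do not settle: a terminal phase starting at 24 h and a log residual SD of 0.10 to 0.20.

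It would be too much to say that later samples fully cure the weakness. The 168 h gain depends on a quantification limit that is not stated, against a prediction of 0.2-1.1 nM. The 96 h sample, at a predicted 2.3-5.6 nM, is the surer one. No dose decision or hypothesis in the plan is shown to turn on the result.

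**What to change.** - Add a plasma sample at the existing 96 h visit to the flow chart in Section 6.0 and to Section 12.3, to be assayed for TFV only.
- Add the same at the existing 168 h visit if the TFV assay's quantification limit allows. That sample would also let the trial check the equating of AUC0-inf with AUC0-168hr in Sections 4.2.2.1 and 4.2.2.2.
- State in Section 8.2.4 that these points enter TFV AUC0-last, AUC0-inf and terminal half-life, and report the extrapolated share of AUC0-inf.
- Make the change in the flow chart itself, not through the flexibility clause in Section 7.1.5.5.

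Cost: collections rise from 12 to 13 or 14, the row from 48 to 52 or 56 mL, and the total from 427.5 to 431.5 or 435.5 mL, inside the 50 mL allowance. With up to 18 subjects this is 18 or 36 further TFV assays. No new visit is needed. Both times fall before 240 h, the earliest planned start of follow-on ART (Section 5.5), so a tenofovir-containing regimen should not normally affect them. If a 168 h value is below quantification, the only loss is the 4 mL and the assay.

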12.4 Algorithm for Assessing Out-of-Range Laboratory Values

For all laboratory values obtained at prestudy (screening) visit and/or pre-dose evaluation:

- A. If all protocol-specified laboratory values are normal, the subject may enter the study.
- B. If a protocol specified laboratory value is outside of the parameter(s) outlined in the inclusion/exclusion criteria (including a repeat if performed), the subject will be excluded from the study.
- C. If ≥ 1 protocol-specified laboratory value not specified in the inclusion/exclusion criteria is outside the normal range, the following choices are available:
 1. The subject may be excluded from the study;
 2. The subject may be included in the study if the abnormal value(s) is not clinically significant (NCS) (the investigator must annotate the laboratory value "NCS" on the laboratory safety test source document).
 3. The subject may be included in the study if the abnormality is consistent with a pre-existing medical condition which is not excluded per protocol (e.g., elevated eosinophil count in a subject with asthma or seasonal allergies) the medical condition should be annotated on the laboratory report or
 4. The abnormal test may be repeated (refer items a. and b. below for continuation of algorithm for repeated values).
 - a. If the repeat test value is within the normal range, the subject may enter the study.
 - b. If the repeat test value is still abnormal, the study investigator will evaluate the potential subject with a complete history and physical examination, looking especially for diseases that could result in the abnormal laboratory value in question. If such diseases can be ruled out, and if the abnormal laboratory value is not clinically relevant, then the subject may enter the study.
- D. If there is any clinical uncertainty regarding the significance of an abnormal value, the subject will be excluded from the study.

12.5 List of Abbreviations Used in this Document

Abbreviation	Definition
AE	Adverse Event
ALT	Alanine Aminotransferase
AST	Aspartate Aminotransferase or All Subjects as Treated
ART	Anti-retroviral therapy
AUC	Area Under the Curve
β-hCG	β-human chorionic gonadotropin
BMD	Bone Marrow Density
BMI	Body Mass Index
BP	Blood Pressure (Systolic or Diastolic)
Bpm	Beats per minute
BT	Body Temperature
CBC	Complete Blood Count
CI	Coordinating Investigator
CL/F	Apparent total clearance of drug from plasma after oral administration
C _{max}	Maximum Plasma Concentration
CRU	Clinical Research Unit
C _{12 hr}	Plasma Concentration at 12 hours post-dose
CV	Cardiovascular
DBP	Diastolic Blood Pressure
DNA	Deoxyribonucleic Acid
ECG	Electrocardiogram
ECI	Event of Clinical Interest
EDC	Electronic data capture
EM	Exposure Margin
EMA	European Medicines Agency
ERB	Ethics Review Board
FBR	Future Biomedical Research
FDAAA	Food and Drug Administration Amendments Act
FSH	Follicle Stimulating Hormone
GCP	Good Clinical Practice
GLP	Good Laboratory Practice

Abbreviation	Definition
GM	Geometric Mean
HIV	Human Immunodeficiency Virus
hr	Hour
HR	Heart Rate
IB	Investigator's Brochure
ICF	Informed Consent Forms
ICH	International Council on Harmonization
IEC	Independent Ethics Committee
IND	Investigational New Drug
IRB	Institutional Review Board
IUD	Intrauterine Device
LDA	Longitudinal data analysis
μM	Micromolar (10 ⁻⁶)
MRL	Merck Research Labs
NCS	Not Clinically Significant
NDA	New Drug Application
NOAEL	No Observed Adverse Event Level
NRTI	Nucleoside reverse transcriptase inhibitor
NNRTI	Non-nucleoside Reverse Transcriptase Inhibitor
PBMC	Peripheral blood mononuclear cell
PE	Physical exam
PK	Pharmacokinetics
PP	Per-Protocol
QP2	Department of Quantitative Pharmacology and Pharmacometrics
QRS	QRS Complex
QT	QT Interval
QTcF	Corrected QT Interval (Fridericia's)
RNA	Ribonucleic acid
RR	Respiratory Rate
RT	Reverse Transcriptase
SAE	Serious Adverse Event
SAP	Statistical Analysis Plan

Abbreviation	Definition
SBP	Systolic Blood Pressure
SOP	Standard Operating Procedure
TAF	Tenofovir alafenamide fumarate
TAM	Thymidine analog mutations
TDF	Tenofovir disoproxil fumarate
TFV-DP	Tenofovir diphosphate
TFV-MP	Tenofovir monophosphate
TFV PD	Tenofovir prodrug
T _{max}	Time to Maximum Concentration
t _{1/2}	Half life
VL	Viral load
VS	Vital Signs

